Pilot Study: The Effect of Intraoperative Ketamine on Analgesia Post-Cardiac Surgery and Prevention of Postoperative Pain

JGH Protocol #: 16-289 NCT02925858

Primary Investigator: [name]

Co-Investigator: [name] [name]

Co-Investigator: [name]

Co-Investigator: [name] [name]

Co-Investigator: [name]

Background

Pain control post-sternotomy is an essential part of fast-track surgery, a program to promote early recovery. Up to 75% of patients complain of moderate-to-severe pain after cardiac surgery, with poorly controlled pain leading to an increased risk of myocardial ischemia and chronic post-sternotomy pain, which is seen in 11% of patients. Given the relative contraindications to epidural analgesia and non-steroidal anti-inflammatories after coronary artery bypass grafting (CABG) surgery, options for multimodal analgesia are limited.

Ketamine is an NMDA antagonist which potentiates the release of inhibitory neurotransmitters, modulating the sensory processing of pain.⁴ Ketamine is a well-established treatment for a variety of pain syndromes, and is approved by Health Canada to be used as a supplemental agent during anesthesia.⁵⁻⁷ There is a growing literature showing that Ketamine contributes to pain control after surgery as well. It has been shown that Ketamine decreases opioid needs after spine surgery, as well as after thoractomy.⁸⁻¹⁰ While these studies used the racemic form of Ketamine, the only version approved for use in Canada, a Finnish study on the cardiac surgery population evaluated the S(+) enantiomer of Ketamine, which has not been available in Canada. This was shown to reduce postoperative opioid requirements by 20%.¹¹

There are limited downsides to the administration of Ketamine. The most common adverse effects of ketamine in awake patients include nightmares, hallucinations, a dissociative state, headaches, and hepatotoxicity. ^{5,12} In clinical studies of low dose Ketamine used for perioperative pain control, there has not been shown to be a significant increase in side effects between treatment and placebo groups. ⁹

Ketamine, while used at times, is not routinely used during cardiac anesthetics. It has not been studied for its effect on postoperative pain control and its effect on post-sternotomy chronic pain.

Given that the S(+) enantiomer of Ketamine previously studied in cardiac surgery patients is not available in Canada, this study will investigate the racemic form of Ketamine that is available in Canada, which, to our knowledge, has not been studied in the cardiac surgery population. This is the form of ketamine will has well established use during anesthesia care and the form of ketamine with which the vast majority of the literature on postoperative pain has been based.

Specific Aim & Hypothesis

The main goal of this pilot study is to assess the effect of an intraoperative intervention, the administration of ketamine, on analgesia post-cardiac surgery. This pilot study will also help assess the feasibility of recruiting and retaining patients, safely administering a blinded medication in the operating room, accurately measuring a primary outcome of postoperative narcotic consumption, and blinding those involved in the care of cardiac surgery patients.

The long-term goal of this study and subsequent follow-up studies is to improve pain control after cardiac surgery, with the hope of allowing patients to perform earlier physiotherapy, regain functional status, and allow for an earlier discharge from hospital.

The specific aim of this study is to ascertain whether an intraoperative infusion of racemic Ketamine can improve postoperative pain control after CABG surgery. The hypothesis is that the intraoperative administration of this medication will improve postoperative pain

control demonstrated through a decrease in postoperative opioid consumption of more than 25%.

Study Design

This is a randomized, blinded, placebo-controlled pilot study. A stratified block randomization procedure will be used to ensure that each group has an equal number of men, and an equal number of women. Blocks will be made in groups of 4 for each sex. Given that the majority of cardiac surgery patients are male, each group is not expected to be made of an equal number of men and women. The randomization procedure will be done with preprepared numbered envelopes. Separate piles of envelopes will be kept to randomize each sex separately. Each envelope will contain the group assignment of either "Ketamine" or "Placebo". Group assignment papers will be inserted in the envelopes in a random order. A list of the group assignment in each numbered envelope will be kept separate from study materials while the study is being carried out. This measure will help ensure that the research coordinator will be blinded during data collection. A separate list will be made by a coinvestigator not involved in the data analysis denoting which envelopes corresponded to "Group A" and "Group B" to allow for the primary investigator to be blinded during data analysis, and for the study coordinator to ensure stratified randomization has distributed an equal number of patients of each sex in each group by the end of the study.

Either the cardiac surgeon, the cardiac anesthetist or a nurse involved in the patients' care will ask the patient if the research coordinator can approach the patient to discuss

inclusion in the study. The research coordinator will then discuss risks and benefits of being included in the study and obtain consent.

On the day of the procedure the research coordinator will randomly select a numbered envelope for the appropriate sex, and hand this to one of the two other co-investigators prior to surgery. One of the two co-investigators will prepare the study drug.

The intervention group will receive Ketamine, while the placebo group will have an identical syringe of normal saline prepared. The placebo will be prepared to blind the cardiac anesthetist caring for the patient. This blinding is important as the quantity of narcotic administered during the surgery is at the anesthetist's discretion, and knowing whether or not a co-analgesic is being administered may affect the quantity of narcotic administered. The quantity of narcotic administered could be considered a co-intervention of the primary outcome, so we are taking all precautions to ensure that the amount of narcotic administered is not influenced by the anesthesiologist's knowledge of the study drug.

The cardiac anesthesiologist will receive the medication in the operating room, delivering a bolus prior to skin incision and administering the medication at a rate determined by the patient's weight. The dose of medication administered should not have any hemodynamic effects, and so unblinding of the cardiac anesthetist should not be necessary. If, for whatever reason unblinding should become necessary, the co-investigator who prepared the medication will make the primary anesthetist aware of the contents of the study drug.

Upon transfer to the intensive care unit, nurses and intensive care physicians will be made aware that the patient is involved in the study. The research coordinator will have documented the volume of study drug administered in the anesthetic record at the end of the

case. If the treatment allocation needs to be known by the intensive care team, they will be able to contact the primary investigator to be immediately unblinded.

Patients will be asked if they would allow the research coordinator to call them at 3 and 6 months after surgery to ask if any pain is present at the site of incision, followed by ten yes or no questions about the pain, and what medications they may be taking for pain, if the pain is still present. These questions can be found in the attached questionnaire.¹⁴

Study Population

The study population will be patients coming for CABG surgery via midline sternotomy at the Jewish General Hospital. This population was selected to ensure all patients have a similar incision and number of chest tubes, two of the main contributing factors to postoperative pain. Patients with a left ventricular ejection fraction less than 50% will be excluded, as these patients are more likely to require a longer duration of circulatory support and mechanical ventilation. Extended mechanical ventilation and sedation will make it difficult to assess the primary outcome of the study. Patients with a history of regular opioid use will be excluded, as these patients have an increased tolerance to opioids and require larger doses to achieve adequate pain control. Including these patients in a small randomized study would risk having a significant effect on the primary outcome. Patients with known hepatic or renal dysfunction will be excluded as well, given the theoretical accumulation of ketamine. Patients with a contraindication to ketamine will also be excluded, such as those with a previous cerebrovascular accident, or with known hypersensitivity to the drug. Patients unable to

provide consent will also be excluded, as the reporting of pain in these patients will likely be unreliable.

Exposure

Exposure will be randomized to an intervention or placebo. The intervention arm will consist of ketamine as a 0.5mg/kg as a bolus, and a 0.5mg/kg/hr infusion throughout the surgery. For an 80kg patient, with a Ketamine concentration of 10mg/mL, this would amount to a 2mL bolus and 2mL of fluid administration per hour of surgery, or approximately 10mL of fluid for the duration of a surgery. The placebo arm will consist of a saline infusion at the same volumes. This dose of ketamine is based on previous studies that have shown effectiveness in surgical populations. The doses at which Ketamine will be administered is not expected to have any hemodynamic effects, and therefore compliance by the anesthesiologist with the treatment is be expected to be near 100%.

Both treatment arms will receive a full cardiac anesthetic in addition to the study intervention. Since the total quantity of intraoperative opioids administered will depend on infusion rate and duration of anesthesia, the total dose administered will be noted for each patient.

Postoperative opioids will be prescribed at a dose and frequency according to the standard postoperative orders for cardiac surgery patients. An intensive care nurse will administer opioids at the doses prescribed on the post-operative orders. This strict protocol for pain management improves the internal validity of the trial, understanding that this may

somewhat decrease external validity in comparison to other centers who do not manage postoperative pain with the same regimen.

Outcomes

The primary outcome is the quantity of opioid administered over the first 48 hours postoperatively. Forty-eight hours was selected as the duration to monitor opioid consumption, as this is the period during which pain post-cardiac surgery has been shown to be most intense. This primary outcome was selected as it will be reliably documented and straightforward to assess, given the strict guidelines for documentation of opioids.

There will be several secondary outcomes. The quantity of opioids used at 24 hours will be noted. Postoperative pain will be measured daily via the "brief pain inventory" by the research coordinator on postoperative days 0, 1, and 2.¹³ Patients will be asked their current pain, the worst and best pain levels throughout the day, as well as their average pain levels. The need for additional analgesic medications will be assessed as a binary outcome for each type of additional medication (NSAIDs, additional opioids, gabapentinoids, etc), measuring whether or not additional agents are added to treat poorly controlled pain. Additional analgesics would likely affect the dose of post-operative opioids administered, making it a co-intervention which may need to be accounted for in the analysis. The presence or absence of postoperative nausea and vomiting requiring treatment, as well as the diagnosis of delirium will be measured as binary outcomes. Intensive care unit and hospital length of stay will be measured in number of days, while the time to extubation, time to first mobilization to a chair, and time to first ambulation will be measured in number of hours after arrival to the intensive care unit through

chart review. While the dose of ketamine used in this study is not likely to cause psychological side effects, the number of patients reporting hallucinations or severe nightmares will be tracked.

On follow-up phone call at 3 and 6 months patients will be asked whether or not they have persistent pain at the site of the sternotomy. Whether or not persistent pain is present will be noted, along with any medications that they may be taking for the pain. If persistent pain is present, they will be asked ten yes or no descriptive questions about the pain concerning to determine if it is neuropathic in origin.¹⁴ The answer to each question, as well as the overall score will be noted.

Confounders

Possible baseline confounders will be tracked to look for differential distribution between intervention groups. These will include age, sex, body mass index, left internal mammary harvesting. We will stratify our randomization by sex to ensure sexes are balanced in the 2 groups, as sex has been shown to be one of the main confounders for postoperative pain. With a relatively small sample size of 80 patients, a differential distribution of confounders between groups is possible, and an adjustment will be done in our analysis for any factor that is differentially distributed. Injuries during cardiac surgery such as rib fracture and dislocation, or fractured sternum may contribute to postoperative pain as well. Unfortunately, these variables often go undetected and cannot be adequately tracked. We will therefore rely on randomization to ensure equal distribution in both groups.

Analysis Plan

While nearly complete compliance is expected with the therapy, an intention-to-treat analysis will be performed in case any unforeseen issues with compliance arise during the study. Continuous data such as postoperative opioid dose, intensive care unit and hospital length of stay, and time to mobilization and ambulation will be evaluated using the t test if it is determined that the means are normally distributed, or the Wilcoxon Rank Sum test if the means are not normally distributed. Ordinal data such as visual analog scale scores and binary data such as need for additional analgesics and the presence or absence of PONV will be evaluated by a Chi-Square test. If confounding is suspected due to baseline differences in the variables noted above, we will perform a propensity score depending on the variable(s) and the size of the difference. As a secondary analysis, data will be analyzed in subgroups by sex to look for any potential difference in response.

Sample Size & Power Analysis

Using the data in the trial evaluating S(+)-Ketamine, an estimate of 125mg of oxycodone over the 48 hours post cardiac surgery was used as a baseline.¹ In this same study, both the intervention and controls groups had standard deviation of oxycodone of 45mg. To detect a decrease in opioid requirements of 25% with a power of 80% and a two-sided alpha of 0.05, a total of 68 patients would be required in the trial, with 34 in each group. For a power of 90%, a total of 90 patients would be required in the trial with 45 patients in each arm. The Jewish General Hospital, a McGill University teaching hospital, performs approximately 600 cardiac surgeries per year, with approximately 350 CABG surgeries via sternotomy. The goal will be to

enroll 80 patients. With the nature of this study and the need for hospitalization post-cardiac surgery, there should be minimal, if any, drop-outs or loss to follow-up, and therefore the sample size of 80 patients should allow for a power of over 80%.

Strengths & Limitations

Strengths of the study include the ability to randomize, and the ability to blind the patients, nurses, anesthesiologists and pain evaluators. This study will be performed at a single center, which allows for easier standardization of therapy, at the same time limiting generalizability of the findings. The primary outcome, opioid use, is easily measurable.

Limitations will include the inter-individual variability in both patient thresholds for analgesia request, and nurse thresholds to administer analgesia. Injury during cardiac surgery may contribute to pain (rib fracture or dislocation), and will not be able to be accurately measured.

Timetable

The Jewish General Hospital currently performs approximately 350 CABG surgeries per year, which is approximately 30 per month. Once ethics approval is obtained, and organizational logistics are arranged, the goal would be to recruit 80 patients over the span of four months. Another 2 to 3 months will likely be required for full data analysis and manuscript preparation.

References

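### The envelope-draw rule does not secure the sex balance that blocks of 4 are meant to give, and the blinded analyst is also the ICU's unblinding contact (minor)

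*Combined protocol and SAP*

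**What the plan says.** All the allocation text is in the Study Design section of the combined protocol and SAP.

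- **Goal.** Stratified blocks are used "to ensure that each group has an equal number of men, and an equal number of women".
- **Blocks and piles.** "Blocks will be made in groups of 4 for each sex". There is one pile per sex: "Separate piles of envelopes will be kept to randomize each sex separately". Assignment papers go into the numbered envelopes in random order. The number of envelopes per pile is not given.
- **Draw.** On the day of surgery, "the research coordinator will randomly select a numbered envelope for the appropriate sex" and hands it to a co-investigator, who prepares the drug.
- **Lists.** The list of assignments is held apart from study materials: "This measure will help ensure that the research coordinator will be blinded during data collection". The A or B label of each envelope stands on another list: "A separate list will be made by a coinvestigator not involved in the data analysis". One purpose of this second list is "to allow for the primary investigator to be blinded during data analysis". Its other stated purpose, due once the study closes, is "for the study coordinator to ensure stratified randomization has distributed an equal number of patients of each sex in each group".
- **Unblinding.** In the operating room, the co-investigator who prepared the drug reveals the allocation. In the ICU, the team contacts the primary investigator for immediate unblinding.

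The Confounders section names sex as a main confounder of postoperative pain and relies on the stratification to balance it. The Analysis Plan adds a secondary analysis by sex.

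**The concern.** Blocks control balance only when one is finished before the next is opened. A random pick from a whole pile ignores block boundaries, so the written draw rule does not deliver the property that the same section promises. The Confounders section and the by-sex analysis both lean on that property.

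The A/B list is the only backstop mentioned. Read after enrolment, it can show an imbalance but cannot remove one. The text does not say when the coordinator receives it.

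The unblinding question is separate. The person who is to analyse the data blinded is also the person the ICU calls to learn an allocation. If that person sees the allocation and can also see the patient's A/B label, the whole A/B code is known.

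**Working it through.** **Context: the plan's own sample size reproduces.** Inputs from Sample Size & Power Analysis: baseline 125 mg, SD 45 mg, decrease 25% (0.25 × 125 = 31.25 mg), two-sided alpha 0.05. A two-sample t test needs 33.54 per arm for 80% power, rounded up to 34 (68 in total), and 44.56 per arm for 90%, rounded up to 45 (90 in total). Both match the plan. The target of 80 is not in dispute.

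**Assumptions.** Each block holds two of each assignment (implied by the goal of equal numbers, not stated). The sex split is 60 men and 20 women; the documents say only that most patients are male. Pile sizes are varied.

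**Block order, or a draw within one open block.** The gap within a sex never exceeds 2, and it is 0 when the number enrolled of that sex is a multiple of 4.

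**Random draw from the pile.** Let a pile hold N envelopes, half for each arm, and let r be left unused at the end. If R of the unused envelopes are ketamine, the gap among patients is |r − 2R|, with R hypergeometric. The gap cannot exceed r. So an exhausted pile gives 0, and a pile with at most 2 left keeps the cap of 2.

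*4 spare per pile.* A gap above 2 requires all four unused envelopes to be from one arm: P = 2·C(N/2, 4)/C(N, 4).
- Men, N = 64: 2 × 35,960 / 635,376 = 0.113
- Women, N = 24: 2 × 495 / 10,626 = 0.093
- At least one sex: 1 − (1 − 0.113)(1 − 0.093) = 0.196, about 20%. The mean gap within a sex is about 1.4 and the maximum is 4.

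*8 spare per pile.* The gap stays at 2 or less only if the unused envelopes split 4–4 or 5–3: P = 1 − [C(N/2, 4)² + 2·C(N/2, 3)·C(N/2, 5)]/C(N, 8).
- Men, N = 68: 0.259
- Women, N = 28: 1 − (1,002,001 + 1,457,456)/3,108,105 = 0.209
- At least one sex: 1 − (1 − 0.259)(1 − 0.209) = 0.413 from unrounded values, about 41%. The mean gap is about 2 and the maximum is 8.

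*Sensitivity to the split.* With 64 men and 16 women and 4 spare per pile (68 and 20 envelopes), the figure is 19%. With 62 and 18 and piles of 64 and 20, it is 0%, because only 2 are left in each.

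**Effect on power.** With 4 spare per pile, the worst total split has both gaps of 4 in the same direction: 36/44. The noncentrality is (31.25/45)·√(n₁n₂/(n₁+n₂)). At 40/40 this is 3.106, power 86.6%. At 36/44 it is 3.090, power 86.3%.

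**Unblinding: the passages side by side.** One part of Study Design blinds the primary investigator during data analysis. A later part makes the same person the ICU's route to immediate unblinding. No relay to a code-holder is written, and nothing says whether the investigator sees the allocation.

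**The case against.** The strongest reply is that little is at stake. Assignment is still random, the gaps are small, power is intact, and the Confounders section already tracks sex and plans adjustment for factors that turn out unbalanced. The probabilities rest on pile sizes and a sex split that the documents do not give: across assumed values they run from 0% to 69%, and the top needs 80 envelopes per sex, far more than the women expected. Drawing at random within an open block also fits the text and would give the blocks a purpose. Strict order has its own cost in predictability.

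Most of this stands, and it sets the weight at minor. It does not remove the point. The section promises to ensure balance, its plain wording does not, and exhausting both piles exactly cannot be planned when the sex mix is unknown.

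A reader might go further and infer that the coordinator will use the A/B list to steer draws and so break concealment. The documents do not support that. The wording on the list reads most naturally as a check at the end of the study, and nothing says that it guides the choice of envelope. Harm would need the list to be available during enrolment, the study coordinator to be the research coordinator who draws envelopes (both terms are used), and draws actually to be steered. Only the silence on timing remains, which justifies a precaution.

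A reader might also infer that the analyst is certain to be unblinded. Being the contact does not mean seeing the code, and harm needs an ICU request in the first place. The primary outcome is charted opioid dose, which limits an analyst's influence. This is a potential conflict only.

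**Conclusion.** The point holds, at minor weight. The written draw rule does not secure the cap of 2 per sex that blocks of 4 can give. Under the assumed 60/20 split, the chance of exceeding it in at least one sex is 0% with piles exactly used up, 20% with 4 spare envelopes per pile and 41% with 8. These figures depend on assumed pile sizes and show that balance is not guaranteed; they do not show that it will fail. It would be wrong to infer that allocation stops being random or that the trial loses meaningful power: the cost at 36/44 is 0.3 percentage points. What is lost is a stated design property that the handling of sex as a confounder and the by-sex analysis rely on.

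The primary investigator's two roles should be reconciled, since no relay step separates them.

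**What to change.** 1. State that envelopes are filled in block order within each sex and that the coordinator takes the next consecutively numbered envelope for that sex, logging number, date and time. Describe the result as a gap of at most 2 per sex, since the last block may be incomplete.
2. State that the A/B list is withheld from the coordinator until enrolment ends. The interim view of balance this gives up is unnecessary under block order.
3. Route ICU unblinding to an existing code-holder who takes no part in the analysis. The co-investigator who makes the A/B list is one candidate, already described as outside the data analysis. The co-investigators who prepare the drug would serve only if they too are kept out of the analysis, which the documents do not say.

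These are wording changes that use existing staff and lists. The code-holder must be reachable while patients are in the ICU.

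The main downside is predictability. With fixed blocks of 4 in order, someone who knows the earlier assignments is certain of the fourth in every block and of the third whenever the first two match (chance 1/3): (1 + 1/3)/4 = 33% of assignments. A best guess is right (1/2 + 2/3 + 2/3 + 1)/4 = 71% of the time, against 50% by chance. Here the people with that knowledge are the co-investigators who prepare the drug, and Study Design does not have them obtain consent or pick envelopes. Varying the block size would reduce the exposure.

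### No intraoperative cardiovascular data are planned, so the assumption of no hemodynamic effect, and that part of the pilot's safety aim, cannot be checked

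*Combined protocol and SAP*

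**What the plan says.** **The aim.** The Specific Aim & Hypothesis section lists what the pilot will help assess the feasibility of, including "safely administering a blinded medication in the operating room". It sets no criterion for *safely*.

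**The assumption.** It is used twice. Study Design: "The dose of medication administered should not have any hemodynamic effects, and so unblinding of the cardiac anesthetist should not be necessary". Exposure says the dosing "is not expected to have any hemodynamic effects, and therefore compliance by the anesthesiologist with the treatment is be expected to be near 100" percent.

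**Data from the period when the drug is running.** There are two items. Under Study Design the research coordinator "will have documented the volume of study drug administered in the anesthetic record" by the end of the case. Under Exposure the total intraoperative opioid dose is noted for each patient.

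**Data from afterwards.** The Outcomes section says: "The presence or absence of postoperative nausea and vomiting requiring treatment, as well as the diagnosis of delirium will be measured as binary outcomes". It adds that "the number of patients reporting hallucinations or severe nightmares will be tracked", and it lists pain scores, added analgesics, time to extubation, mobilization times and lengths of stay.

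**Not listed anywhere.** Blood pressure, heart rate, vasopressor or inotrope use, general adverse events, changes to the infusion with their reasons, and a count of unblindings.

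**The concern.** The protocol treats the absence of hemodynamic effects as settled, and draws two operational expectations from it: no need to unblind the anesthetist, and near-complete compliance. It also says that, to the authors' knowledge, racemic ketamine has not been studied in the cardiac surgery population. A pilot is a natural place to check such an assumption, and this one has an aim that covers it.

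Followed exactly, the plan would end with no data for or against the assumption. If an anesthetist slowed the infusion after a pressure change, the record would show a volume but no reason. If a visible response led to unblinding, the plan would not require that to be counted. A report that the drug was given safely in the operating room would, for its cardiovascular part, rest on the assumption and not on observation.

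**Working it through.** **1. The plan's own figure.** Inputs from Sample Size & Power Analysis: control mean 125 mg oxycodone, SD 45 mg, 25% decrease, two-sided alpha 0.05, equal groups.

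- Difference = 0.25 × 125 = 31.25 mg; standardized effect = 31.25 / 45 = 0.694.
- Two-sample t test: 33.5, rounded up to 34 per group (68 total) for 80% power; 44.6, rounded up to 45 per group (90 total) for 90% power. Both match the plan.
- With 80 patients, 40 per arm, power is 86.6%, consistent with the stated figure of over 80%.

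No number in the plan is wrong on this point. What carries forward is 40 per arm.

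**2. What the plan relies on, against what it records.**

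| Statement relied on | What would check it | Planned? |
|---|---|---|
| No hemodynamic effects | Heart rate, pressure, vasoactive drug use, by arm | No |
| Unblinding not needed | Count of unblindings, with reasons | Route provided; no count or reason |
| Near-complete compliance | Delivered against expected volume; reasons for changes | Delivered volume only |
| Safe operating-room administration | A criterion, and data from that period | No criterion; volume and opioid dose only |

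**3. What volume alone can show.** Take the worked volumes in Exposure for an 80 kg patient: 2 mL, then 2 mL per hour. A recorded total of 8 mL fits three cases:

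- a full 3-hour infusion at 80 kg: 2 + 2 × 3 = 8;
- a 4-hour operation at 80 kg with the infusion stopped after 3 hours: 8;
- a full 4-hour infusion in a 64 kg patient (illustrative weight): (64 / 80) × (2 + 2 × 4) = 8.

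Weight and infusion duration would separate these cases. Only the reason for a shortfall would then be missing.

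The expected volume is itself ambiguous. In Exposure, 0.5 mg/kg × 80 kg = 40 mg, which at 10 mg/mL is 4 mL, but the text gives 2 mL. The same twofold gap applies to the hourly rate. Over 4 hours the two statements imply 4 + 4 × 4 = 20 mL and 2 + 2 × 4 = 10 mL. They must be reconciled before any expected volume is computed.

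**4. What 40 per arm could show.** The documents give no event rates and no SD for pressure, so these are assumptions.

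- Zero events in 40: upper 95% bound = 1 − 0.05^(1/40) = 7.2% one-sided, or 1 − 0.025^(1/40) = 8.8% two-sided.
- Chance of at least one event in 40, 1 − (1 − p)^40: 33%, 55%, 87% and 98.5% for true rates of 1%, 2%, 5% and 10%.
- Power to compare arms: 13% for 5% against 10%; 24% for 10% against 20%.
- Difference in mean pressure change, 95% half-width = 1.991 × SD × √(2/40) = 1.991 × SD × 0.2236: about 4.5 mmHg for SD 10 and 6.7 mmHg for SD 15.

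Such data describe. They do not establish absence of effect.

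**The case against.** The case against has real force.

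- **Blinding.** A reader might infer that blinding depends on the hemodynamic assumption. It does not. Study Design bases it on an identical saline syringe. The assumption supports only the expectation that unblinding will not be needed, and routes to unblind are given for the operating room and intensive care.
- **Primary comparison.** A reader might infer that it is compromised. The Analysis Plan specifies intention-to-treat in case compliance fails. The intraoperative opioid dose, which the protocol says knowledge of the drug could influence, is recorded.
- **Volume.** A reader might infer that a shortfall could never be interpreted. Weight sets the rate, and the body mass index listed under Confounders requires it. Operating times are probably charted. That comparison is possible but not planned, and it would still lack a reason.
- **The aim.** It concerns feasibility and is not a cardiovascular safety endpoint. Delirium, hallucinations or nightmares, nausea and vomiting, and time to extubation bear on it in part. To say the aim cannot be answered at all would go too far.
- **Ischemia and stroke.** A reader might infer that these must be outcomes. Background speaks of "poorly controlled pain leading to an increased risk of myocardial ischemia", which ties ischemia to pain and not to ketamine. Study Population excludes patients with a contraindication, "such as those with a previous cerebrovascular accident", but excluding a history does not oblige a trial to record new events.
- **Prior evidence.** The reference list includes a study of lung and heart surgery whose title reports no harmful hemodynamic effects of ketamine. The protocol does not cite it at either hemodynamic statement or compare its dosing.

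These points narrow the concern. None supplies intraoperative cardiovascular data, reasons for changes or unblindings, or a criterion for *safely*.

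**Conclusion.** The concern holds in a limited form. The planned data cannot check the assumption of no hemodynamic effect or answer the intraoperative cardiovascular part of the safety aim. The other parts of that aim are partly covered by postoperative outcomes, and the primary analysis stands.

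The effect is on what the pilot can report, not on any stated number. Even with the data added, 40 per arm would not prove safety: zero events would remain compatible with a true rate of up to 7.2% (one-sided) or 8.8% (two-sided). Nor would the pressure comparison amount to a test of no effect, because the SD of 10 to 15 mmHg is assumed and no margin is defined.

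This rests on equal allocation of the 80 patients, and on the protocol text being the full list of what will be collected.

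**What to change.** In Outcomes, add a descriptive secondary safety outcome, reported by arm with confidence intervals, from the anesthetic record and the chart review already planned:

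1. Heart rate and arterial pressure before the bolus, at a fixed time after it, and at prespecified times during the infusion.
2. Intraoperative vasopressor or inotrope use, as yes/no and as a total.
3. Any reduction, interruption or early stop of study drug, and any unblinding, with time and reason; plus weight and infusion duration, so that delivered volume can be compared with expected volume.

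State how *safely* will be judged. Reword the hemodynamic statements in Study Design and Exposure as an assumption to be checked. Reconcile the mg/kg and mL statements in Exposure before computing an expected volume. Counts of postoperative myocardial ischemia or infarction and of stroke are optional and descriptive only.

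Cost: a protocol amendment, a few more data fields and slightly more abstraction time per patient. This assumes the values are already charted, in which case no new procedure is needed.
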